6.0 PATIENT SELECTION

6.1 Inclusion Criteria

1. Adult participants aged 18-55 years (inclusive at the time of screening).
2. No prior history of major organ or systemic disease including diabetes, hypertension, kidney, heart or liver disease. Participants with childhood asthma are acceptable.
3. Normal hematology, clinical chemistry and urinalysis parameters at screening, unless not deemed clinically significant by the investigator.
4. Body Mass Index (BMI) between 18 kg/m² and 32 kg/m² (inclusive)
5. Taking no prescription medications 2 weeks prior to admission or over-the-counter medications 7 days prior to admission. Occasional use of paracetamol or ibuprofen (up to 1000 mg and 400 mg/day respectively) are acceptable. Routine vitamins and supplements are permissible at the discretion of the investigator.
6. Able to allow intravenous medication to be administered.
7. Males (along with their female partners) and females of childbearing potential (defined as a female who is not menopausal or surgically sterilized) must be willing to use an acceptable method of birth control during heterosexual activities including a condom and a second highly effective method (i.e., hormonal contraceptive, intra-uterine device) or abstinence for the duration of the study. Should a woman become pregnant or suspect she is pregnant while participating in this study, she must inform her treating physician immediately. Males and females should continue with the aforementioned contraception for 90 days after the last dose.
8. Able to understand and willing to sign an ethics committee-approved written informed consent document
9. Non-smokers. Social and light smokers of up to 10 cigarettes per day who can abstain from smoking during the confinement period and have no evidence of underlying lung disease (bronchitis, COPD or reactive airways disease).
10. Willing to remain abstinent from alcohol 24 hours prior to admission and until after the confinement period in the unit.

6.2 Exclusion Criteria

1. A history of cardiovascular disease, diabetes or hypertension (Screening assessment >150/90 after 5 minutes sitting), significant neurological, pulmonary (including asthma), hepatic, rheumatic, autoimmune, haematological, metabolic or renal disorder.
2. Prescription medications are prohibited. No prescription medications 2 weeks prior to admission or over-the-counter medications 7 days prior to admission. Occasional use of paracetamol or ibuprofen (up to 1000 mg and 400 mg/day respectively) are acceptable. Routine vitamins and supplements are permissible at the discretion of the investigator
3. Any moderate or severe allergies, including anaphylaxis, to food, drugs or environmental allergens. Mild allergies such as hayfever may be included.
4. Females who are pregnant or lactating. Women of childbearing potential must have a negative pregnancy test within 14 days of study initiation and at baseline.

5. Consumption of caffeine 48 hours prior to start of study treatment and whilst confined to the unit.
6. History of any psychiatric illness or psychological disorder which may impair the ability to provide written informed consent or participate in the study
7. Clinically significant abnormal laboratory value at screening as determined by the Investigator.
8. Participant is sero-positive to HIV-1 or HIV-2, HCV or HBV.
9. History or presence of alcoholism within two years prior to the first study drug administration or drugs of abuse unless it can be explained to the satisfaction of the investigator that it is due to a standard dose of a prescribed medication and that an adequate wash-out will occur prior to admission as per inclusion #5
10. No findings on clinical examination that, in the opinion of the investigator, could compromise the safety of the participant or the results of the study.
11. Blood donation or significant blood loss within 60 days prior to the first study drug administration.
12. Administration of investigational product in another trial within 30 days prior to the first study drug administration or five half-lives, whichever is longer.
13. Surgery within the past 3 months prior to the first study drug administration determined by the PI to be clinically relevant.
14. Active malignancy or history of malignancy in the past 5 years

6.3 Enrollment and Randomization

52 participants will be enrolled in the study. 8 participants will be randomly selected to a substitution list to be used in the event of drop-out. Block randomization method will be used for remaining participants with a sample number of 8/group and a 3:1 treatment:placebo ratio. A Randomization Plan will be created, and the randomization of eligible study participants will be managed as per the plan. A Randomization and Substitution List will be prepared using a statistical software package.

6.4 Blinding

Participants and the study investigators/personnel will be blinded. This is a third-party blinded study whereupon the pharmacist (or designate) preparing the LSALT peptide or placebo for infusion will be unblinded.

6.5 Inclusion of Women and Minorities

Both men and women and members of all races and ethnic groups are eligible for this trial.

7.0 STUDY PROCEDURES

This single center study is a double-blind, placebo-controlled, randomized, single and multiple ascending dose phase I study of LSALT peptide safety, tolerability, and pharmacokinetics.

7.1 Single Ascending Dose (SAD) Cohort

7.1.1 Sample Size. The study sample size will be 4 + 24 participants for the SAD arm of the protocol. The first 4 participants will comprise a low dose escalation cohort, and 3 cohorts of 8 (6 treatment and 2 placebo) will comprise the single ascending dose cohorts.

7.1.2 LSALT Peptide Dosing. It is anticipated that seven single intravenous doses of LSALT peptide (0.01 mg, 0.1 mg, 0.3 mg, 0.5 mg, 1 mg, 2.5 mg and 5 mg) will be administered in this arm of the study.

The first 4 participants will each sequentially receive a single escalating low dose of the LSALT peptide (0.01 mg, 0.1 mg, 0.3 mg or 0.5 mg). Escalation to the next dose and participant will occur every 72 hours if no adverse effects are seen. Participants will then be enrolled in cohorts of 8 and randomized to treatment or placebo in a 3:1 ratio. The dose for the first SAD cohort will be 1 mg administered intravenously once over 2 hours. The first 2 subjects of each cohort will be sentinels (1 treatment, 1 placebo). Continuation of the study in each cohort will occur if no clinical or biochemical adverse effects are observed in the sentinels as determined by the Safety Review Committee (SRC). Escalation to the higher dose cohorts (2.5 mg and 5 mg) will occur after 10-14 days if no clinical or biochemical adverse effects are observed in the prior cohort.

A rationale for the proposed doses is based on the NOAEL in dogs (2.5 mg/kg) and the minimum effective dose in mice (0.1-1 μ g/kg). The human equivalent dose is 1.4 mg/kg. The 1 mg dose (16.7 μ g/kg in a 60 kg human) is 1200-fold less than the maximum tolerated dose of 20 mg/kg in dogs, 150-fold lower than the NOAEL and provides a safety factor of 83 relative to the calculated human equivalent dose. The 5 mg dose (83.3 mcg/kg in a 60 kg human) is 240-fold less than the maximum tolerated dose of 20 mg/kg in dogs, 30-fold less than the NOAEL and provides a safety factor of 17 relative to the calculated human equivalent dose. Based on the minimum therapeutic dose observed in mice (0.1 - 1 μ g/kg), a conservative first dose of 0.01 mg (166.7 ng/kg in a 60 kg human) is chosen to further increase the safety margin of the starting dose by 100-fold (i.e. 8400 x less than the human equivalent dose calculated from the NOAEL).

7.1.3 Confinement. Participants will be confined for 24 hours following infusion of the LSALT peptide or placebo.

7.1.4 SAD Study Procedures

- **Day -29. Pretreatment Evaluation and Randomization.** 28 days prior to study initiation, enrolled participants will undergo informed consent, followed by a complete history and physical examination (including body weight and height) including seated vital signs (temperature, Blood Pressure, pulse oximetry Respiratory rate and Heart Rate), drugs of abuse and an alcohol breath test, baseline fasting laboratory studies (CBC, clinical chemistry), Coagulation profile (INR and PTT), urinalysis, 12-lead electrocardiogram (Supine) and chest x-ray (Single PA view). Women of child-bearing age will have a β -hCG to rule out pregnancy. Participants will then be randomized.

Low dose cohort

- **Day -1 Admission.** Participant 1 will undergo a clinical evaluation including vital signs, complete physical examination (including body weight and height), 12-lead

electrocardiogram, drugs of abuse and alcohol breath test, urinalyses, 25 ml of blood drawn for safety laboratory investigations including CBC, clinical chemistries, Coagulation profile (INR and PTT), and women of child-bearing age will have urine pregnancy test to rule out pregnancy.

- **Day 1. First Dose.** Participant 1 will undergo a clinical evaluation including vital signs. Participant 1 receives a single infusion of the LSALT peptide, 0.01 mg administered over 2 hours. Clinical evaluation, including vital signs, symptom directed physical examination, 12-lead electrocardiogram and 25 ml of blood will be drawn for laboratory investigations, including CBC, clinical chemistries and coagulation profile (INR and PTT), 24 hours post the end of infusion. If the participant shows no adverse events, they will be discharged from the unit on Day 2.
- **Day 4. Follow up.** Participant 1 returns for an outpatient follow up visit. Adverse events are recorded, clinical evaluation including vital signs, complete physical examination, urinalyses, 12-lead electrocardiogram and 25 ml of blood drawn for safety laboratory investigations including coagulation profile (INR and PTT),
- **Day 4. Admission.** Participant 2 will undergo a clinical evaluation including vital signs, complete physical examination, 12-lead electrocardiogram, drugs of abuse and alcohol breath test, urinalysis, 25 ml of blood drawn for safety laboratory investigations including CBC, clinical chemistries, coagulation profile (INR and PTT) and women of child-bearing age will have a urine pregnancy test to rule out pregnancy.
- **Day 5. Dose escalation.** Participant 2 will undergo a clinical evaluation including vital signs. Participant 2 receives a single infusion of the LSALT peptide, 0.1 mg administered intravenously over 2 hours. Clinical evaluation, including vital signs, symptom directed physical examination, 12-lead electrocardiogram ,and 25 ml of blood will be drawn for laboratory investigations, including CBC, clinical chemistries and coagulation profile (INR and PTT) 24 hours post the end of infusion. If the participant shows no adverse events, they will be discharged from the unit on Day 6.
- **Day 8. Follow up** Participant 2 returns for an outpatient follow up visit. Adverse events are recorded, clinical evaluation including vital signs, a complete physical examination, urinalyses, 12-lead electrocardiogram and 25 ml of blood drawn for safety laboratory investigations including coagulation profile (INR and PTT).
- **Day 8 Admission:** Participant 3 will undergo a clinical evaluation including vital signs, complete physical examination, 12-lead electrocardiogram, drugs of abuse and alcohol breath test, urinalyses, 25 ml of blood drawn for safety laboratory investigations including CBC, clinical chemistries and coagulation profile (INR and PTT) and women of child-bearing age will have a urine pregnancy to rule out pregnancy.
- **Day 9. Dose escalation.** Participant 3 will undergo a clinical evaluation including vital signs. Participant 3 receives a single infusion of the LSALT peptide, 0.3 mg administered intravenously over 2 hours. Clinical evaluation, including vital signs, symptom directed physical examination, 12-lead electrocardiogram and 25 ml of blood will be drawn for laboratory investigations, including CBC, clinical chemistries and coagulation profile (INR and PTT) 24 hours post the end of infusion. If the participant shows no adverse events, they will be discharged from the unit on Day 10.
- **Day 12 Follow up:** Participant 3 returns for an outpatient follow up visit. Adverse events are recorded, clinical evaluation including vital signs, complete physical examination, urinalyses, 12-lead electrocardiogram and 25 ml of blood drawn for safety laboratory investigations including coagulation profile (INR and PTT).

- **Day 12 Admission:** Participant 4 will undergo a clinical evaluation including vital signs, complete physical examination, 12-lead electrocardiogram, drugs of abuse and alcohol breath test, urinalyses, 25 ml of blood drawn for safety laboratory investigations including CBC, clinical chemistries, coagulation profile (INR and PTT) and women of child-bearing age will have a urine pregnancy test to rule out pregnancy.
- **Day 13. Dose escalation.** Participant 4 will undergo a clinical evaluation including vital signs. Participant 4 receives a single infusion of the LSALT peptide, 0.5 mg administered intravenously over 2 hours. Clinical evaluation, including vital signs, symptom directed physical examination, 12-lead electrocardiogram and 25 ml of blood will be drawn for laboratory investigations, including CBC, clinical chemistries, coagulation profile (INR and PTT) 24 hours post the end of infusion. If the participant shows no adverse events, they will be discharged from the unit on Day 14
- **Day 16 Follow up.** Participant 4 returns for an outpatient follow up visit. Adverse events are recorded, clinical evaluation including vital signs, complete physical examination, urinalyses, 12-lead electrocardiogram and 25 ml of blood drawn for safety laboratory investigations including coagulation profile (INR and PTT).

Treatment and Assessment Timetable (Low Dose)

Participant	Study Day	1				2				3				4			
		-1	1	2	4	4	5	6	8	8	9	10	12	12	13	14	16
In patient period		X	X			X	X			X	X			X	X		
Informed consent		X															
Vital signs	X	X	X ¹	X	X	X	X ¹	X	X	X	X ¹	X	X	X	X ¹	X	X
Physical Exam	X	X		X	X	X		X	X	X		X	X	X		X	X
Alcohol Breath test	X	X				X				X				X			
Drugs of Abuse	X	X				X				X				X			
Urinalysis	X	X		X	X		X	X		X		X	X		X		X
CBC	X	X		X	X	X		X	X	X		X	X	X		X	X
Chemistry	X	X		X	X	X		X	X	X		X	X	X		X	X
Creatinine/eGFR	X	X		X	X	X		X	X	X		X	X	X		X	X
LFTs	X	X		X	X	X		X	X	X		X	X	X		X	X
INR/PTT	X	X		X	X	X		X	X	X		X	X	X		X	X
CXR	X																
ECG	X	X	X ²		X	X	X ²		X	X	X ²		X	X	X ²		X
B-hCG ³	X	X			X	X			X	X			X	X			X
Adverse Event	X	X	X	X	X	X	X	X	X	X	X	X	X	X	X	X	X
LSALT Administration			X				X				X				X		
Discharge from unit				X				X				X				X	
Follow up					X				X				X				X

Note: Fasting for blood sampling required for Screening and post dose Follow up. Participants will be required to have fasted from all food and drink except water for at least 8 hours prior to blood sampling.

1. Vital signs dosing day (seated): pre dose (+/-30 mins), 1 hour (+/- 10mins), 2 hour (+/- 10 mins) 6 hours (+/- 15min) and 10 hours post completion of infusion (+/- 30 mins).
2. 12 lead electrocardiogram (supine): pre dose (+/- 30 mins), 2 hours (+/- 15 mins) and 8 hours post completion of infusion (+/- 30 mins)
3. Pregnancy test will be via serum B-hCG at Screening and a urine pregnancy test at pre dose (Study Day -1, Day 4, Day 8, Day 12) and follow up.

SAD Cohorts

- **Day -1.** Admission to unit; Participants will undergo a clinical evaluation including complete vital signs and physical examination, 12-lead electrocardiogram (supine), drugs of abuse and alcohol breath test, urinalyses and 25 ml of blood drawn for safety

laboratory investigations including CBC, clinical chemistries, coagulation profile (INR and PTT) and women of child-bearing age will have a urine pregnancy test to rule out pregnancy.

- **Day 1. Cohort 1.** Participants will undergo a clinical evaluation, including vital signs and 12-lead electrocardiogram .5 ml of blood will be drawn at 30 prior to LSALT peptide infusion for baseline PK measurements. LSALT peptide infusion will begin and run over 2 hours. 5 ml of blood will be drawn at 15 minutess, 30 minutes, 1, 2, 4, 6, 8, and 12 hours after the LSALT infusion has started.
- **Day 2.** Participants will undergo a clinical evaluation, including vital signs and symptom directed physical examination. 25 ml of blood will be drawn for laboratory investigations, including CBC, clinical chemistries, coagulation profile (INR and PTT) and 24 hour PK sample. An ECG will also be completed. If the participant shows no adverse events, they will be discharged from the unit.
- **Day 4.** Participants will undergo a clinical evaluation, including vital signs and a symptom directed physical examination. 25 ml of blood will be drawn for laboratory investigations, including 72 hour PK sample. An ECG will also be completed.
- **Day 7.** Participants will return for a clinical evaluation, including vital signs and a complete physical examination. 25 ml of blood will be drawn for laboratory investigations, including CBC, clinical chemistries and PK. A urinalysis, CXR and ECG will also be completed. Women of child-bearing age will have a urine pregnancy test to rule out pregnancy
- **Day 14. Cohort 2.** Conducted as per Cohort 1 to day 7.
- **Day 28. Cohort 3.** Conducted as per Cohort 1 to day 7.

Treatment and Assessment Timetable (SAD)

Study Day	Screen -29 to -2	-1	1	2	4	7
In patient period		X	X			
Informed consent	X					
Vital signs	X	X	X ⁴	X	X	X
Physical Exam	X	X		X	X	X
Alcohol Breath Test	X	X				
Drugs of Abuse ⁶	X	X				
Urinalysis	X	X		x		X
CBC	X	X		X		X
Chemistry	X	X		X		X
Creatine/eGFR	X	X		X		X
LFTs	X	X		X		X
PK			X ¹	X ²	X ³	X
INR/PTT	X			X		
CXR	X					X
ECG	X	X	X ⁵	X	X	X
B-hCG ⁷	X	X				X
Adverse Event	X	X	X	X	X	X
LSALT Administration			X			
Discharge from unit				X		
Follow up					X	X

Note: Fasting for blood sampling required for Screening and post dose Follow up. Participants will be required to have fasted from all food and drink except water for at least 8 hours prior to blood sampling.

1. PK blood samples: 5 ml of blood will be drawn at 30 mins pre (+/- 5 mins) and 15 mins (+/- 5 mins), 30 mins (+/- 5 mins), 45 mins (+/- 5 mins), 1h (+/- 5 mins), 2h (+/- 5 mins), 4h (+/- 10 mins), 6h (+/- 10 mins), 8h (+/- 10 mins), and 12h (+/- 30 mins) after the LSALT infusion has completed
2. PK blood sample: 24 hours (+/- 30 mins) after infusion has completed
3. PK blood sample: 72 hours (+/- 30 mins) after Infusion has completed

4. Vital signs dosing day (seated): pre dose within 30 mins prior to infusion start), 1 hour (+/- 10mins), 2 hour (+/- 10 mins) 6 hours (+/- 15min) and 10 hours post completion of infusion (+/- 30 mins)
5. 12 lead electrocardiogram (supine): pre dose (+/- 30 mins), 2 hours (+/- 15 mins) and 8 hours post completion of infusion (+/- 30 mins)
6. Repeat Drugs of Abuse (DoA) is permitted at the discretion of the Investigator
7. Pregnancy test will be via serum B-hCG at Screening and a urine pregnancy test at pre dose (Study Day -1/Day 12) and follow up

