7.2.5 MAD Study Procedures

- **Day -29. Pretreatment Evaluation and Randomization.** 29 days prior to study initiation, enrolled participants will undergo informed consent, followed by a complete history and physical examination (including body weight and height) vital signs (seated), alcohol breath test, drugs of abuse test, baseline fasting laboratory studies (CBC, clinical chemistry) including coagulation profile (INR and PTT), urinalysis, 12-lead, electrocardiogram (supine) and chest x-ray (single PA view). Women of child-bearing age will have a β -hCG to rule out pregnancy. Participants will then be randomized.
- **Day -1.** Admission to unit. Participants will undergo a clinical evaluation including complete vital signs and physical examination, 12-lead electrocardiogram (supine), drugs of abuse and alcohol breath test, urinalyses, 25 ml of blood drawn for safety laboratory investigations including CBC, clinical chemistries, urinalysis and women of child-bearing age will have a urine pregnancy test to rule out pregnancy.
- **Day 1.** Participants will undergo clinical evaluation including vital signs. 5 ml of blood will be drawn at 30 minutes prior to LSALT peptide infusion for baseline PK measurements. LSALT peptide infusion will begin and run over 2 hours. 5 ml of blood will be drawn at 15, 30, 45 60, 75, 90, 105, 120, 125, 130, 135, 140 minutes, and 3 hours from the onset of the LSALT infusion.

- **Day 2.** Participants will undergo a clinical evaluation, including vital signs, a brief history and symptom directed physical exam. 25 ml of blood will be drawn for laboratory investigations, including CBC, clinical chemistries and coagulation profile (INR and PTT), urinalysis and 24 hour PK sample (from the onset of the first LSALT infusion). An ECG will also be completed. If the participant shows no adverse events, they will receive the second dose of the LSALT peptide.
- **Day 3.** Participants will undergo a clinical evaluation, including vital signs, a brief history and a symptom directed physical exam. If the participant shows no adverse events, they will receive the third dose of the LSALT peptide. 5 ml of blood will be drawn at 15, 30, 45 60, 75, 90, 105, 120, 125, 130, 135, 140 minutes, and 3 hours from the onset of the LSALT infusion.

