1. PK blood samples: 5 ml of blood will be drawn at 30 prior to LSALT peptide infusion for baseline PK measurements. LSALT peptide infusion will begin and run over 2 hours. 5 ml of blood will be drawn at 15, 30, 45 60, 75, 90, 105, 120, 125, 130, 135, 140 (+/- 2 min) minutes, 3 hours (+/- 5 min) from the onset of the LSALT infusion
2. PK blood sample: 24 hours (+/- 30 mins) from the onset of the 1st infusion.
3. PK blood samples: 5 ml of blood will be drawn at 30 prior to LSALT peptide infusion. LSALT peptide infusion will begin and run over 2 hours. 5 ml of blood will be drawn at 15, 30, 45 60, 75, 90, 105, 120, 125, 130, 135, 140 (+/- 2 min) minutes and 3 hours (+/- 5 min) from the onset of the LSALT infusion
4. PK blood sample: 72 hours (+/- 30 mins) from the onset of the first LSALT infusion
5. PK blood sample: 96 hours (+/- 30 mins) from the end of the third LSALT infusion
6. Vital signs dosing day (seated): pre dose (+/-30 mins), 1 hour (+/- 10mins) , 2 hour (+/- 10 mins) 6 hours (+/- 15min) and 10 hours post completion of infusion (+/- 30 mins)
7. 12 lead electrocardiogram (supine): pre dose (+/- 30 mins), 2 hours (+/- 15 mins) and 8 hours post completion of infusion (+/- 30 mins)
8. Pregnancy test will be via serum B-hCG at Screening and a urine pregnancy test at pre dose (Study Day -1,) and follow up

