8.1. PK Sampling Schedule

SAD:

PK blood samples: 5 ml of blood will be drawn at 30 minutes pre (+/- 5 minutes) and 15 minutes (+/- 5 minutes), 30 minutes (+/- 5 minutes), 45 minutes (+/- 5 minutes), 1h (+/- 5 minutes), 2h (+/- 5 minutes), 4h (+/- 10 minutes), 6h (+/- 10 minutes), 8h (+/- 10 minutes), and 12h (+/- 30 minutes) after the LSALT infusion has completed; followed by 24h and 72h samples.

MAD:

Day 1 PK blood samples: 5 ml of blood will be drawn at 30 minutes pre start of infusion (+/- 5 minutes) and 15 minutes (+/- 5 minutes), 30 minutes (+/- 5 minutes), 45 minutes (+/- 5 minutes), 1h (+/- 5 minutes), 2h (+/- 5 minutes), 4h (+/- 10 minutes), 6h (+/- 10 minutes), 8h (+/- 10 minutes), and 12h (+/- 30 minutes) after the LSALT infusion has completed; followed by 24h sample.

Day 3 PK blood samples: 5 ml of blood will be drawn at 15 minutes (+/- 5 minutes), 30 minutes (+/- 5 minutes), 45 minutes (+/- 5 minutes), 1h (+/- 5 minutes), 2h (+/- 5 minutes), 4h (+/- 10 minutes), 6h (+/- 10 minutes), 8h (+/- 10 minutes), and 12h (+/- 30 minutes) after the 3rd LSALT infusion has completed; followed by 72h and 92h samples.

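### The PK sampling clock is contradictory between and within protocol and SAP, SAP 8.2 does not define time 0, and neither MAD schedule supports every planned parameter

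*Protocol*

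**What the plan says.** **SAD, Day 1**

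- Protocol 7.1.4, Day 1 text: "15 minutess, 30 minutes, 1, 2, 4, 6, 8, and 12 hours after the LSALT infusion has started".
- Protocol 7.1.4, timetable footnote 1: adds a 45-min sample and ends "8h (+/- 10 mins), and 12h (+/- 30 mins) after the LSALT infusion has completed". Footnotes 2 and 3 count the 24-h and 72-h samples from completion too.
- SAP 8.1: "8h (+/- 10 minutes), and 12h (+/- 30 minutes) after the LSALT infusion has completed; followed by 24h and 72h samples". The SAD PK listing shell in SAP 16 also labels samples from the end of infusion.
- Protocol 7.3.6: a 15–140 min and 3 h list from onset that is not limited to MAD, with the 24-h and 72-h samples from onset for SAD and MAD alike.
- Protocol 15.0: 0.5 to 24 h after drug administration for both parts, with no statement of start or end.
- On SAD Day 7, Protocol 7.1.4 says "25 ml of blood will be drawn for laboratory investigations, including CBC, clinical chemistries and PK", and its timetable agrees. SAP 8.1 lists no such sample.

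**MAD**

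- Protocol 7.2.5, text and timetable, Days 1 and 3: samples at 15 to 140 "minutes, and 3 hours from the onset of the LSALT infusion". The next samples are at 24 h and 72 h from the first onset.
- SAP 8.1: 15 min to 12 h after completion on both days. On Day 3 this is "after the 3rd LSALT infusion has completed; followed by 72h and 92h samples".
- Last sample: "PK blood sample: 96 hours (+/- 30 mins) from the end of the third LSALT infusion" in the 7.2.5 timetable, 96 h from the third onset in 7.3.6, and 92 h in SAP 8.1.
- Day 3 pre-dose sample: present in timetable footnote 3 ("3. PK blood samples: 5 ml of blood will be drawn at 30 prior to LSALT peptide infusion"), absent from the 7.2.5 Day 3 text and from SAP 8.1.

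**Analysis**

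- SAP 8.2 uses the linear trapezoidal rule from time 0, without saying what time 0 is, and takes Cmax and Tmax as observed.
- SAP 11 computes interim parameters from scheduled times.
- SAP 12 records no changes from the protocol.

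**The concern.** Plasma concentrations and PK parameters are the secondary endpoints (SAP 4.2). With a 2-hour infusion, a nominal time means something 2 h different on each clock, so Tmax, each AUC and the meaning of Cmax depend on which passage was followed. A programmer working from SAP 8.1 and 8.2 cannot tell how to place the samples on the time axis. If the MAD cohorts were sampled as Protocol 7.2.5 says, several AUCs that SAP 8.2 and 8.4 call for have no data across most of their interval.

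**Working it through.** The documents give no figure to reproduce here. The contradictions follow from setting the passages side by side. Their size needs a model.

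**Inputs.** Infusion 2 h (Protocol 10.1.6). Rat half-life 0.66–1.17 h, at 100–450 mg/kg (Protocol 3.5). No human half-life or quantification limit is given, so half-life is varied up to 4 h as an assumption. Model: one compartment, constant-rate input, first-order elimination with k = ln 2 / t½. Concentrations are in units of the infusion's steady-state level, so true AUC0-inf = 2.

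**1. Cmax on the completion clock.** The first post-dose sample is 15 min after the end, so observed Cmax / peak = 2^(−0.25/t½).

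| t½ (h) | 0.66 | 1.17 | 2 | 4 |
|---|---|---|---|---|
| Observed / peak | 0.769 | 0.862 | 0.917 | 0.958 |

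The shortfall is 23%, 14%, 8% and 4%. Over the ±5 min window it is 16–30% at 0.66 h and 9–18% at 1.17 h. The start and onset lists each have a sample at 2 h (120 min), so in this model they capture the peak.

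**2. Effect on the slope.** With one schedule at every dose, ln(observed Cmax) = ln(peak) − 0.25k. The second term does not depend on dose, so the power-model slope for Cmax under linear PK remains 1.00. Under assumed quantification limits of 0.1–10% of the 1 mg peak, the AUC0-inf slope is 1.00–1.02 and the AUC0-t slope 1.00–1.15. The SAP 8.4 criterion with p = 5/1 is 1 + ln(0.5)/ln(5) = 0.569 to 1 + ln(2)/ln(5) = 1.431.

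**3. Time 0.** Take the completion-clock samples through 12 h after completion, with the pre-dose zero placed at time 0. Trapezoidal AUC as a share of true AUC0-inf:

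| t½ (h) | 0.66 | 1.17 | 2 |
|---|---|---|---|
| Times converted to hours from start | 0.728 | 0.868 | 0.927 |
| Post-completion times read as hours from time 0 | 0.391 | 0.569 | 0.698 |

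The second row is what an interim would produce if the scheduled times in SAP 8.1 were used unconverted.

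**4. The 3–24 h gap on the Protocol 7.2.5 schedule.** On Day 1 nothing lies between 3 h and 24 h. On Day 3 the sample after 3 h is the one 72 h from the first onset. With doses 24 h apart, that is 72 − 48 = 24 h from the third onset.

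- *24-h value below the limit, and so set to missing under SAP 8.3.* AUC0-t stops at 3 h and covers 0.858, 0.677 and 0.490 of true AUC0-inf at 0.66, 1.17 and 2 h.
- *24-h value quantifiable.* The trapezoid draws one straight line across 21 h. At t½ = 3.5 h (k = 0.198), peak = 1 − 2^(−2/3.5) = 0.327. Then C(3 h) = 0.327 × 2^(−1/3.5) = 0.268 and C(24 h) = 0.327 × 2^(−22/3.5) = 0.0042. The trapezoid area is 21 × (0.268 + 0.0042)/2 = 2.86, against a true area of (0.268 − 0.0042)/0.198 = 1.33. AUC0-inf becomes 176% of true, and AUC0-12 read off the line 144%. At 4 h they are about 164% and 137%.

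AUC0-12, AUC0-24 and AUC0-tau all cross this gap. AUC0-24 and AUC0-tau also enter the MAD power model in SAP 8.4.

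**The case against.** Several points on the other side stand.

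- **Time 0 is less open than it looks.** SAP 10.2 counts adverse events as treatment-emergent from the time of first administration, which makes sense only if that is infusion start. The listing shell also measures duration from administration and labels the pre-dose sample relative to the start. Infusion start is the sensible reading, and the definition is a one-line clarification. It is still needed, because SAP 11 uses scheduled times and SAP 8.1 counts those from completion.
- **For SAD Day 1, most sources agree.** The timetable (with windows), SAP 8.1 and the shell all say completion. The outliers are the 7.1.4 text and the generic 7.3.6 list.
- **Document versions may explain the MAD mismatch.** SAP 2 cites Protocol V3 and an addendum that is not among the documents reviewed. That cannot explain a conflict between text and timetable within Protocol 7.1.4.
- **Cmax is defined as the maximum observed concentration.** Missing the peak is therefore a limit of sampling, not an analysis error.

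A reader might go further and infer that SAD–MAD comparisons are biased, or that the power model must not be run. The documents do not support either. SAP 6.1 presents each study part separately and no SAD–MAD comparison is planned. A modelled MAD/SAD AUC0-t ratio has no stable direction either: with an assumed limit of 1% of peak it moves from 0.40 to 1.96 as half-life goes from 3 to 3.5 h. Protocol 3.8 proposes the 5 mg MAD cohort for additional PK data, but nothing says that cohorts within a part were sampled differently. Even if they were, dropping a prespecified exploratory model would be a debatable trade-off, and flagging it is enough.

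**Conclusion.** The point holds, and should be fixed before the final analysis. The contradictions are a matter of text and need no assumptions: SAP 8.1 and the protocol cannot both be followed, and the protocol disagrees with itself for SAD Day 1 and for the anchor of the last MAD sample. SAP 12 does not acknowledge the differences.

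The direction of the Cmax shortfall on the completion clock follows from constant-rate infusion with first-order elimination. Its size (14–23% at rat half-lives, 4–8% at 4–2 h) is illustrative and rests on one compartment and assumed human half-lives. It largely cancels in the slope when one schedule applies throughout a study part.

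The lack of support for MAD AUC0-12, AUC0-24 and AUC0-tau applies only to cohorts sampled on the Protocol 7.2.5 schedule. The percentages given for it also depend on the unknown quantification limit. The endpoints are secondary and the dose-proportionality assessment is exploratory, so this concerns analysis and reporting, not the primary safety conclusions.

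**What to change.** 1. Reconcile Protocol 7.1.4 (text and timetable), 7.2.5, 7.3.6 and 15.0 with SAP 8.1 to the schedule actually used in each cohort, and state it by cohort in SAP 8.1. Settle 92 h versus 96 h and its anchor, the Day 3 pre-dose sample and the SAD Day 7 sample.
2. In SAP 8.2, define time 0 as the start of infusion for each profile. Use actual elapsed times in the final analysis. At any interim, convert scheduled times to hours from infusion start.
3. Where no sample was taken during or at the end of infusion, footnote Cmax as the maximum observed post-infusion concentration.
4. For any MAD cohort sampled as in Protocol 7.2.5, do not report AUC0-12. Flag AUC0-24, AUC0-tau, and any AUC0-t or AUC0-inf that uses the 24-h point, as resting on a 3–24 h gap.
5. If cohorts within one study part used different schedules, still run the exploratory power model, but flag it and report the time of the last quantifiable sample by dose.

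The cost is wording corrections, a few footnotes and a little extra PK programming. No new samples are required.
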